4.1 Overview

We will evaluate the impact and feasibility of TPE versus RACD as a surveillance and response strategy in the communities around passively detected index cases using a cluster-randomized trial umbrella study design. To facilitate operations of the trial and subsequent roll-out of the TPE intervention should it be shown to be effective and feasible, the randomization will occur at the administrative level of the locality. A total of 77 historically at-risk study localities or clusters will be included in the trial; 39 will be randomized to the TPE intervention, and 38 to the control intervention (RACD) (Figure 4). If new malaria hotspots are detected during the study period, these additional localities may also be included in the study at the discretion of the study team, in consultation with the Swaziland National Malaria Control Programme. These additional study localities will be randomly assigned to receive either the RACD or the TPE intervention. Target areas for localities randomized to receive TPE will be defined as all individuals residing within 200m of an index case that is detected in passive surveillance and resides in a TPE locality, with individuals residing immediately beyond 200m included if a minimum of 30 individuals are not enrolled within 200m. Target areas for localities randomized to receive RACD will be defined as all individuals residing within 500m of an index case that is detected in passive surveillance and resides in a RACD locality (as per current policy in Swaziland), while focusing on maximizing coverage within the immediate 200m radius around the index case. Per current policy, for individuals receiving RACD, blood will be collected for RDT and DBS and subjects testing positive on RDT will be referred to a local clinic for treatment with AL. In the TPE arm, blood will not be collected and presumptive treatment will be administered by modified DOT. Incidence data will be collected passively during the study period. For secondary outcome measures, in select Target Areas, a pill count will be conducted 7-10 days after the first visit day and a qualitative Acceptability Assessment will be conducted with study participants at the time of the pill count. Passive monitoring for serious adverse events (SAEs) will occur in both the TPE and the RACD arms. To measure prevalence and seroprevalence, a cross sectional survey will be conducted in Target Areas near the end of the study (during the end-line survey, expected to take place mid 2017). Finally, to validate the serological markers, a follow-up survey will be conducted at 6-9 months among any individuals who were infected at baseline (index cases in both arms as well as secondary cases detected by RDT at baseline in the RACD arm).

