Appendix X:	Qualitative questionnaires for the Acceptability Assessment – Focus Groups with Malaria Surveillance Team
Appendix Y:	Swaziland Malaria Elimination Advisory Group (SMEAG) Terms of Reference
Appendix Z:	TPE Safety Monitoring Committee Terms of Reference

Study summary

Title	Evaluating the effectiveness and feasibility of reactive targeted parasite elimination (TPE) vs. reactive case detection (RACD) as a community-level intervention in response to a passively identified index case in Swaziland
Study design	Cluster randomized controlled trial
Aims	
Primary aim: To compare the impact of TPE versus RACD on malaria incidence.
 
Secondary aims
 
Effectiveness:
 
 1. To compare the impact of TPE versus RACD on seroprevalence. 2. To compare the impact of TPE versus RACD on prevalence of infection. 3. To compare the impact of TPE versus RACD on proportion of imported incident cases. 4. To compare the impact of TPE versus RACD on time to first post-intervention incident local case. 5. To compare the impact of TPE versus RACD on transmission potential as measured by relatedness of infections by microsatellite genotyping. 
Feasibility:
 
 1. To determine the feasibility of reaching 80% coverage for TPE versus RACD. 2. To evaluate the safety of TPE versus RACD. 3. To compare the acceptability of TPE versus RACD. 4. To compare the costs and cost-effectiveness of TPE versus RACD. 5. To measure the adherence to modified DOT with DP in the TPE arm.
Study site	Eastern endemic region of Swaziland, a very low endemic malaria elimination setting. A total of 287 health facilities and their catchment areas are located in this area.
Time frame	September 2015 until two transmission seasons completed (mid-2017)
Cluster or unit of randomization	At risk localities will be randomized to either TPE or RACD using a block stratified randomization based on risk rank (1-3) and population
Target area	For TPE localities: Neighborhood of individuals residing within 200m of an index case detected in passive surveillance. Individuals residing immediately beyond 200m will be included if a minimum of 30 individuals are not enrolled within 200m. For RACD localities: Neighborhood of individuals residing within 500m of an index case detected in passive surveillance.

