
4.2 Study site and study population

The control and test interventions for this study will take place in the eastern half of Swaziland where RACD is currently conducted and focus in 77 localities (or sub-districts) which contains 431 EA (enumeration areas) but only 139 historically at-risk EA (Figure 4). To recruit Target Areas, the study will utilize the existing health infrastructure throughout Swaziland. Laboratory confirmed index cases present through passive surveillance and are reported through a toll free "977 Hotline." Health facilities are shown in Figure 5. Although all index cases are targeted for a follow-up case investigation (questionnaire with capture of GPS coordinates at the home of the index case), only index cases residing in the study localities will be enrolled in the study. Index cases not residing in study localities will not directly contribute to the study, but samples from these cases will also be genotyped (see section 12.7) to allow for more accurate classification of study subjects as having acquired their infection locally vs. being imported based on circulating parasite genotypes. Both locally acquired and imported cases can trigger the study intervention. The six catchment areas are covered by different surveillance agents with one officer covering Vuvulane and Ndzevane (Lubombo region) and another officer covering the other four catchment areas.

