9.1 Overview

Prior to implementing the intervention in each Target Area, a baseline blood survey will only be conducted in the RACD arm. Blood testing will not be performed pre-intervention in the TPE arms as the trial was designed to be operationally relevant so that feasibility (coverage, acceptability, etc.) could be assessed. In both the TPE and RACD arms, a follow-up blood survey will be conducted toward the end of the study during the end-line survey, expected to take place mid 2017. In index and secondary cases and a subset of RDT-negative control subjects from the RACD arm, a follow-up survey will also be conducted at 6-9 months for serological assessment. Finally, using routine health facility data from blood draws in symptomatic individuals, incidence data will be collected for the entire study period. Locality level incidence data will be collected over the entire study period.

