9.4 Passive collection of incidence data

Incidence data from each locality will be collected passively for the entire study period starting from the first incident case reported in that locality. As this data will be de-identified and is part of standard surveillance, IRB approval will not be necessary for this data collection. Incidence data will be collected as: incidence of local cases (not counting the first case), proportion of imported cases (a surrogate measure of R_c [27]), and time to first end-line local incident case.

10 Acceptability Assessment

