14.2 Outcome measures

Table 6. Outcome measures

Outcome	Indicator
Primary Aim	
Incidence	Cumulative incidence of all cases (Pf infection) identified by passive surveillance in the locality subsequent to the first reported case during the study period (not including additional cases found through RACD). Cases include both locally acquired and imported infections.
Secondary aims (effectiveness)	
Exposure (seroprevalence)	Seroprevalence to markers of recent exposure using ELISA in end-line survey samples taken from residents in Target Areas near the end of the study (expected mid 2017), excluding index cases detected through passive surveillance.
Infection prevalence	Prevalence of infection by LAMP and QTNASBA testing for gametocytes in LAMP positives in end-line survey samples taken from residents in Target Areas near the end of the study (expected mid 2017), including index cases detected through passive surveillance.
Time to first local post-intervention incident case	Time to first incident local case in the Target Area subsequent to the intervention. Target Areas that receive a repeat intervention will qualify to be included again at subsequent interventions.
Proportion of imported incident cases	Proportion of imported incident cases in the locality subsequent to the first reported case will be measured through passive surveillance. Additional cases found through RACD will not be included.
Transmission potential (by genotyping)	Microsatellite genotyping will be performed on samples collected from index cases as well as secondary cases.
Secondary aims (feasibility)	
Coverage	Proportion of persons residing within approximately 200m (TPE localities) or 500m (RACD localities) of the index case who consented to participate in the study and who completed the initial procedures for their study arm (finger prick for RDT in the RACD arm, initial dose of DP in the TPE arm)
Adherence	Proportion of persons who completed 3 days of therapy among all individuals initiated on DP in the TPE arm, as assessed by pill count
Prevalence of SAEs related to treatment	Proportion of subjects experiencing SAEs deemed possibly, probably, or definitely related to DP or AL, out of the total number of subjects enrolled
Acceptability	Qualitative assessment (See Section 10)
Cost	Cost per index case-level intervention, cost per case averted.

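### For localities added and randomised mid-study, the primary count is not tied to randomisation and, read literally, includes cases from before allocation

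*Combined protocol and SAP*

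**What the plan says.** Section 4.1 randomises 77 localities (39 TPE, 38 RACD) and then leaves the list open: "If new malaria hotspots are detected during the study period, these additional localities may also be included in the study". Inclusion is at the study team's discretion, in consultation with the national malaria programme. On allocation it says: "These additional study localities will be randomly assigned to receive either the RACD or the TPE intervention". It gives no start of follow-up for them.

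The primary outcome in Table 6 (section 14.2) is the cumulative incidence of all cases "identified by passive surveillance in the locality subsequent to the first reported case during the study period". Section 9.4 has incidence data "collected passively for the entire study period starting from the first incident case reported in that locality", and section 9.1 says: "Locality level incidence data will be collected over the entire study period". The study summary gives one calendar window for the whole trial, September 2015 to mid-2017.

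The nearest text pointing the other way is in section 4.2: "Index cases not residing in study localities will not directly contribute to the study". Section 14.4 has no rule for added localities: no cut-off date, no term for date of entry, no sensitivity analysis.

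**The concern.** For the original 77 localities the counting rule makes sense. They are allocated at the outset, the first case triggers the assigned response, and later cases can be attributed to that response. A locality added part-way through differs. Its first case in the study period may come well before its allocation, and the rule then picks up every passive case after that one, including those before an arm existed.

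Such cases cannot have been affected by the allocation. Section 4.4 describes RACD as standard of care in all receptive areas, and the case investigation form in Appendix C lists RACD as a response in receptive non-study localities. In a receptive locality later assigned to TPE, the earlier cases would therefore have arisen under control conditions but be scored as TPE outcomes. What is at stake is the size and precision of the primary effect estimate, and whether two analysts would build the same primary dataset.

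**Working it through.** **The texts side by side**

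1. Entry of new localities: during the study, after a hotspot is detected (4.1).
2. Start of the count: the locality's first reported case in the study period (Table 6, 9.4).
3. Study period: one calendar window, not defined per locality (study summary, 9.1).
4. Result of 1 to 3: an added locality with n passive cases between the start of the study period and its randomisation contributes n − 1 cases to the primary outcome from before randomisation.
5. Section 4.2 excludes cases residing outside study localities, but does not say whether a locality's earlier cases become eligible once it is added.

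**Illustration of size**

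The plan gives no number of added localities and no count of their earlier cases, so there is no plan figure to reproduce. Inputs for the base:

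- 200 index cases in total (14.1) and 66 in TPE (14.3, coverage), so 200 − 66 = 134 in RACD. This is not the 134 of section 4.4, which is all index cases per study year.
- 63 localities with at least one case, 22 of them expected in TPE (14.1), so 63 − 22 = 41 in RACD.
- One first case per locality is not counted: RACD 134 − 41 = 93; TPE 66 − 22 = 44; ratio 44/93 = 0.47.

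The plan's inputs do not fit together perfectly: 41 exceeds the 38 localities randomised to RACD. Two other bases are therefore shown. One caps RACD at 38; the other splits the 63 evenly (31.5 per arm).

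Assumption: 5 cases before randomisation per added hotspot, so 5 − 1 = 4 counted. Only these cases are added; the hotspots' later cases are left out.

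| Base (RACD, TPE events) | Base ratio | One in TPE, share of TPE count | Two in TPE | One in each arm |
|---|---|---|---|---|
| 93, 44 | 0.47 | 4/44 = 9% | 52/93 = 0.56 | 48/97 = 0.49 |
| 134 − 38 = 96, 44 | 0.46 | 4/44 = 9% | 52/96 = 0.54 | 48/100 = 0.48 |
| 134 − 31.5 = 102.5, 66 − 31.5 = 34.5 | 0.34 | 4/34.5 = 12% | 42.5/102.5 = 0.41 | 38.5/106.5 = 0.36 |

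Range for the assumed number of earlier cases (first base, two hotspots in TPE):

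- 1 earlier case each: none counted, ratio stays at 0.47.
- 2 each: (44 + 2)/93 = 0.49.
- 10 each: (44 + 18)/93 = 0.67.

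These are ratios of event counts, not of incidence. Two added localities also enlarge the TPE denominator. With equal-sized localities, the 52/44 = 1.18-fold rise in the TPE count becomes 1.18/(41/39) = 1.12 if all 39 TPE localities form the denominator, or 1.18/(24/22) = 1.08 if only the 22 with cases do.

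**Dilution from the plan's own hypothesis**

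Take a true ratio of 0.50 and B = 31.5 × 656 × 0.004 = 82.7 RACD cases. Add a localities per arm, each with m counted cases before randomisation and m afterwards under RACD (0.5m under TPE). The observed ratio is (0.5B + 1.5am)/(B + 2am).

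- a = 2, m = 5: 56.3/102.7 = 0.55.
- a = 8, m = 20: 281.3/402.7 = 0.70.
- Counting from randomisation only: 0.50 in both.

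**Chance imbalance**

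Three added localities under simple randomisation all fall in one arm with probability 2 × 0.5³ = 0.25. With 10 counted earlier cases each and no later cases, the true 0.50 becomes (41.3 + 30)/82.7 = 0.86 if all go to TPE, and 41.3/(82.7 + 30) = 0.37 if all go to RACD.

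**The case against.** The strongest reply is that the plan never says outright that earlier cases are counted. Under section 4.2 a case that arose before its locality joined was not then in a study locality, so it might be left out. That reading is possible and rules out saying that the plan definitely counts these cases. It does not settle the matter, because section 4.2 is silent on localities that join later while Table 6 and section 9.4, taken as written, include the cases.

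Second, hotspot has no case threshold. Section 1.2 describes hot spots by risk of future infection, and Table 6 excludes cases found through RACD. A hotspot could be recognised with few countable earlier cases. This stands: five is an assumption. It is not extreme, since 23 of the 77 localities in Table 2 had at least five incident cases between September 2012 and March 2015, but that window is longer than the trial.

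Third, a reader might infer that discretionary entry by a study team that knows the case counts lets it favour one arm. The documents do not support that. The arm is assigned at random after the decision to include, the national programme is consulted, and section 4.3 has randomisation done by someone not directly involved in field activities.

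Fourth, a reader might want added localities removed from the primary analysis altogether. They are validly randomised, and excluding them sits awkwardly with the intention-to-treat approach in section 14.4. Counting from randomisation removes the problem without that step.

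**Conclusion.** The point holds as a conflict in the counting rule. Read literally, Table 6 and section 9.4 score cases from before randomisation as outcomes in any locality added under section 4.1; section 4.2 hints otherwise without resolving it. The problem is contingent: it exists only if localities are added and have more than one passive case beforehand.

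Since allocation of added localities is random, the expected effect is dilution towards no difference, with extra variance and possible chance imbalance in either direction. It is not a systematic advantage to one arm.

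On the assumed 5 earlier cases per hotspot, the shift is small for one hotspot per arm (0.47 to 0.49) and moderate for two in TPE (0.47 to 0.56 on event counts, less on incidence). The larger shifts shown above need many added localities, many earlier cases or an unlucky split. All these sizes rest on assumed inputs. The ambiguity does not, and because it affects the primary outcome it should be closed before analysis.

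**What to change.** In Table 6 and section 9.4, state that for any locality added after the start the randomisation date is recorded, and that outcome cases and time at risk are counted only from the first index case after that date. That index case takes the place of the uncounted first case in the original localities. Add a matching sentence to section 4.2 so that the passages agree.

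In section 14.4, keep added localities in the primary intention-to-treat comparison on this footing, and add a sensitivity analysis restricted to the 77 localities randomised at the start.

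The cost is a few sentences of wording and one extra analysis. The downside is that a few earlier cases go uncounted and added localities have shorter follow-up. The 77 localities on which the power calculation rests are unaffected.

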For individuals <18 years of age, informed consent will be obtained from one parent or guardian, as is customary in Swaziland. Assent for adolescents 12-17 years of age will be obtained, as is customary in Swaziland.

Table 4. Informed Consents

Subject/Activity	Informed consent covers	
Index case	
 No informed consent as case investigation (questionnaire and DBS collection for malaria testing) is part of standard surveillance. 	
Resident Enrollment, Intervention (Appendices E, F) 
 All residents of Target Areas 	RACD	TPE
	
 At enrollment: 
 Brief questionnaire and GPS mapping. Intervention blood testing with RDT & referral to health facility if RDT positive. Storage of blood with DBS, and with microtainer collection in RDT positives. 	
 At enrollment: 
 Brief questionnaire and GPS mapping. If eligible for DP, 3 day course of DP by modified DOT. If not eligible for DP, blood testing by RDT & referral to health facility if RDT positive. Storage of blood with DBS, and with microtainer collection in RDT positives. 7-10 days post intervention: 
 Potential pill count.
6-9 month Follow-up (Appendix L) 
 All Index cases residing in Target Areas. All secondary cases and some RDT-negative controls from RACD localities. 	
 At 6-9 months after diagnosis (Note: The study team will seek consent to collect a 6-9 month sample from index cases and RDT-positive residents who were diagnosed within in the 9 months prior to study launch): 
 Follow-up blood testing with RDT & referral to health facility if RDT positive. Storage of blood with microtainer and DBS. 	
End-line survey (Appendix N) 
 All residents of Target Areas. 	
 At end-line survey, end of study: 
 Brief questionnaire and GPS mapping. Follow-up blood testing by RDT & referral to health facility if RDT positive. Storage of blood with DBS. Brief interview. 	

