If an individual cannot safely be given DP, that individual will not be given medication for presumptive treatment. Pregnant women and breastfeeding women will be excluded. All girls ≥ 10 years of age will also be asked about menses. Those who have had menarche but have not menstruated in the past 4 weeks will also be excluded. Infants < 9 months of age or < 7 kg will also be excluded. For infants and children unable to take tablets, drugs will be crushed, mixed with water and administered as a suspension. No more than two courses of DP may be given within a 12-month period. Additionally, a second course of DP should not be given within 2 months after the first course due to the long elimination half-life of piperazine. Other contraindications include: severe malaria, young children who vomit (electrolyte disturbances can increase QTc), heart problems or rhythm disturbances, kidney or hepatic insufficiency, recent treatment with certain medications (antiarrhythmics, neuroleptics, antibiotics, non-sedating antihistamines, antimalarial agents, and others (cisapride, droperidol, domperidone, bepridil, dephemanil, probucol, levomethadyl, methadone, vinca alkaloids, and arsenic trioxide).

Individuals who cannot safely be given DP will be tested by RDT using the *Pf*-specific First Response RDT during the intervention visit. At the time that blood is collected for RDT testing, the same finger prick will be used to generate a slide and dried blood spot. Four spots of blood will be collected for each DBS. A second finger prick will be used to collect microtainer blood samples from RDT-positive individuals. Subjects testing positive by RDT will be referred to the closest health facility for treatment with a drug that is safe for them according to national policy.

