DP was evaluated for use as IPT in schoolchildren in Uganda in a trial comparing DP, sulfadoxine-pyrimethamine (SP), and amodiaquine + sulfadoxine-pyrimethamine (AQ+SP), to placebo.[11] In this study of 780 children, those receiving DP were at no higher risk of adverse events than those receiving placebo. In another recent study of IPT in schoolchildren using DP in Uganda, no safety concerns were identified. The most commonly reported adverse events in this study were cough, headache, and abdominal pain, but children receiving DP monthly or once a term were at no higher risk for these events than those receiving placebo. There was also no difference in the risk of anorexia, nausea, vomiting, diarrhea, or pruritus between the groups[21].

In general, ACTs are not recommended for use in the first-trimester of pregnancy due to insufficient safety data.[41] In second and third trimester, ACTs may be used with the exception of DP, for which safety data in late pregnancy are lacking. A recent review of published data on 945 women exposed to an artemisinin during pregnancy, including 123 during first trimester, and 822 during the second or third trimester, did not identify an association between use of artemisinins and adverse pregnancy outcomes.[41] However, these studies were limited by small sample sizes and lacked power to detect rare serious adverse events and heterogeneity between studies precluded pooled analysis.

To minimize any safety risks associated with DP treatment, we plan to exclude all pregnant or breastfeeding women as well women who have experienced menarche, but no menses in the past 4 weeks from DP treatment. Due to limited data in infants <9 months of age or <7kg, these subjects will also be excluded from DP treatment. Individuals excluded from DP treatment will be given an RDT to determine if they have a malaria infection, and will be advised to seek treatment at their health facility if they test positive for malaria. In addition, we will monitor for SAEs.

Blood draws:

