- *If yes, ask: Where did you sleep overnight, when did you sleep there, why did you sleep there, and personal protection? If slept outside Swaziland, also ask about means of travel and border post of re-entry.*

Within Swaziland				
Town / Locality / Inkhundla	Duration of Stay		Reason for sleeping away from current residence: -previous residence -business -holiday -visiting friends/family -other (specify, _____)	Personal protection -chemoprophylaxis (specify___) -bednet -mosquito repellent or coil -None
	First Night YY/MM/DD	Last Night YY/MM/DD		
a.				
b.				
c.				
d.				
e.				

Outside of Swaziland							
Country	Province / Town	Duration of Stay		Reason for sleeping away from current residence: -previous residence -business -holiday -visiting friends/family - Other (specify_____)	Personal protection (specify___) -chemoprophylaxis -bednet -mosquito repellent or coil -None	Means of travel -Large bus -Kombi (van) -Personal car -Ride share (catch a ride/got a lift) -Airplane -Bicycle -Walked -Other (specify_____)	Border Post of Re-Entry - Lavumisa/Golela - Salitje/Onverwacht - Mahamba - Gege/Bothashoop - Sicunusa/Houtkop - Sandlane/Nerston - Ngwenya/Oshoek - Bulembu/Josefsdal - Matsamo/Jeppe's Reef - Mananga - Lomahasha/Namaacha - Mhlumeni/Goba - KMIII International Airport - Other
		First Night YY/MM/DD	Last Night YY/MM/DD				
a.							
b.							
c.							
d.							
e.							

Medical History

10. *Weight:* ___ . ___ kg

Tablet should make this question compulsory for all ages

Ask the following questions to assess for potential criteria excluding participant from receiving antimalarial medication:

11. Are you pregnant or breastfeeding? Yes No Don't know

12. Have you menstruated in the past but not within the past 4 weeks? Yes No Don't know

13. Are you less than 9 months of age? Yes No Don't know

Tablet should automatically complete this question based on date of birth, select an option and not allow Agent to make changes

14. Are you allergic to have had a past adverse reaction to DP? Yes No Don't know

15. Have you already taken 2 courses of DP in the past year? Yes No Don't know

16. Have you taken DP within the last 2 months? Yes No Don't know

17. Do you have heart, kidney, or liver problems? Yes No Don't know

18. Does your family have a history of heart problems or sudden death? Yes No Don't know

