19. In the past month have you taken antimalarial drugs for either treatment or prevention of malaria (mefloquine, halofantrine, lumefantrine, chloroquine, or quinine)? Yes No Don't know

20. Have you had a fever in the past 48 hours, or are otherwise feeling ill? Yes No Don't know

If Yes, was subject taken to local health facility? Yes No

21. Are you currently taking any medications? Yes No Don't know

If Yes, are you taking any of the following medications? (check all that apply)

a. Medicines that effect heart rhythms (such as amiodarone, disopyramide, dofetilide, ibutilide, procainamide, quinidine, hydroquinidine, or sotalol)

b. Medicines that treat depression

c. Medicines that treat mental health problems (such as phenothiazines, sertindole, sultopride, chlorpromazine, haloperidol, mesoridazine, pimozone, or thioridazine)

d. Medicines that treat infection (macrolides [such as erythromycin or clarithromycin], fluoroquinolones [such as moxifloxacin or sparfloxacin], medicines for fungal infections [such as imidazole and fluconazole], as well as pentamidine [used to treat a specific type of pneumonia] and saquinavir [for treatment of HIV])

e. Antihistamines used to treat allergies or inflammation (such as terfenadine, astemizole, mizolastine)

f. Medicines that treat stomach problems such as cisapride, droperidol, domperidone, or diphemanil

g. Medicines to treat cancers (vinca alkaloids, arsenic trioxide), chest pain (bepridil), drug addiction (levomethadyl, methadone), and high cholesterol levels (probucole)

Drug Administration: (Subject is eligible to receive medication if they weigh at least 7kg and answered "No" to questions 10-19 and are not taking any of the medications listed in 20a-20g)

22. Is the subject eligible to receive medication? Yes No

Tablet to automatically say Yes or No for eligibility of individual to receive medication based on responses above and criteria provided, options should be greyed out (disabled).

a. *If yes, indicate regimen administered:*

Check one	Weight band	Color of box	Regimen administered	Subscription
	7-12 kg	Bottle	320 mg piperazine /40 mg dihydroartemisinin tablets, 3 half tablets	½ tablet daily x 3 days
	7-12 kg	Pink box	160 mg piperazine /20 mg dihydroartemisinin tablets, 3 tablets	1 tablet daily x 3 days
	13-23 kg	Green box	320 mg piperazine /40 mg dihydroartemisinin tablets, 3 tablets	1 tablet daily x 3 days

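### The Appendix K rule that fixes DP eligibility on the tablet is off by one question, and question 22 has no 'If no' branch for the RDT that section 7.3 requires

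*Combined protocol and SAP*

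**What the plan says.** **Blood in the TPE arm.** The overview in 4.1 states: "In the TPE arm, blood will not be collected and presumptive treatment will be administered by modified DOT". Section 7.3 gives the procedure for residents who cannot take DP: "Individuals who cannot safely be given DP will be tested by RDT using the *Pf*-specific First Response RDT during the intervention visit". It adds a slide and a dried blood spot from the same finger prick, referral of positives, and a further sample: "A second finger prick will be used to collect microtainer blood samples from RDT-positive individuals". The TPE column of Table 4 (section 6.3) reads "If not eligible for DP, blood testing by RDT & referral to health facility if RDT positive", and 17.3 reads "Individuals excluded from DP treatment will be given an RDT to determine if they have a malaria infection".

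**DP eligibility.** Just before question 22, Appendix K makes a resident eligible if the weight is at least 7 kg and the answers are 'No' "to questions 10-19 and are not taking any of the medications listed in 20a-20g". At question 22 the instruction is: "Tablet to automatically say Yes or No for eligibility of individual to receive medication based on responses above and criteria provided". The answer options are then disabled, so the agent cannot change them.

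**What follows question 22.** There is one branch, 'If yes', leading to the regimen (22a) and whether the first dose was observed (22b). There is no 'If no' branch.

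**The concern.** Table 3 bars DP for people with fever or other illness and for those recently treated with QT-prolonging drugs. The tablet rule is a main control that applies these exclusions in the field, to people who are mostly well and take the drug presumptively. A rule that points to the wrong questions could weaken that control without anyone noticing, because staff cannot override question 22.

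Section 17.3 lists the substitute RDT among the measures for people excluded from DP. If the form neither prompts the test nor holds its result, the study cannot readily show who was tested, who was positive and who was referred. The RACD forms do hold this information, so the two arms' records would differ.

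**Working it through.** No sample-size or power figure is involved. The check sets the rule beside the printed form.

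**1. Which numbers are the form's own.** The first yes/no exclusion is printed as "11. Are you pregnant or breastfeeding". The travel item skips to question 10, which is weight, and the pill-count table refers to the regimen as 22a. Both agree with the printed numbering. (Numbers 12 and 13 are also printed on two travel items, so a rule keyed to numbers is fragile in any case.)

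**2. Rule against form.**

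| Item | Content on the form | Treatment by the rule |
|---|---|---|
| Q10 | Weight in kg | Cited as needing 'No', which is impossible |
| Q11-Q19 | Nine yes/no exclusions; Q19 is recent antimalarials | Cited |
| Q20 | Fever in past 48 hours or feeling ill | Not cited |
| 20a-20g | Not on the form | Cited |
| 21a-21g | Seven drug groups | Not cited |

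**3. The intended rule.** The range 10-19 spans 19 - 10 + 1 = 10 questions; the yes/no exclusions Q11-Q20 number 20 - 11 + 1 = 10. Both letter ranges run a to g, which is 7. The counts match, so one shift of one place explains both references. The intended rule is almost certainly 11-20 and 21a-21g, covering 10 + 7 = 17 items. Weight is already handled by the separate 7 kg condition.

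**4. What different readings would do.**
- Strictly as written: Q10 cannot be answered 'No', so nobody is eligible and the rule fails on first test.
- Q10 skipped, drug list recognised as 21a-21g: 9 + 7 = 16 of 17 items are applied; only Q20 is lost.
- Q10 skipped, drug list left unlinked: 9 of 17 are applied; Q20 and the seven drug groups are lost.
- Both references shifted by one: all 17 are applied.

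**5. The missing branch.** Section 7.1 assigns blood results to the RACD household form and drug doses to the TPE form. Appendix I question 11 has fields for RDT result, referral and blood spot, and the Appendix H neighborhood dashboard counts RDTs, positives, microtainers and referrals. Appendix K has no such fields, and the Appendix J dashboards count medication but no RDTs. Nothing says that Appendix I is to be used for DP-ineligible residents in the TPE arm. Section 12.3 lists who gives microtainer blood and does not mention them.

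**6. Scale of the substitute test (illustration only).** Section 1.3 gives 42 RDT positives in 8355 screened: 42 / 8355 = 0.5%, or about 0.5 positives per 100 residents tested. The DP-ineligible share is not stated. Assume 10% to 25%, and read the 1782 in 14.3 as people treated, as it is worded. Then 1782 x 0.10 / 0.90 = 198 to 1782 x 0.25 / 0.75 = 594 residents are due an RDT, giving about 1 to 3 positives over the trial. The rate comes from general screening and could be higher among people excluded for fever.

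**The case against.** A reader might infer that the tablet would clear febrile residents, or those on QT-prolonging drugs, to receive DP. The documents do not support that as the outcome. Strictly applied, the rule passes nobody. Wrong clearance requires reading the rule loosely at question 10 and literally at question 20. A programmer who notices question 10 may well shift the whole block, and the form has only one a-to-g drug list. The lock instruction also refers to the responses above it, which include questions 20 and 21.

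There are other safeguards. Question 20 has a sub-item on whether the person was taken to a health facility, and 7.4 requires referral of sick people. Question 19 asks about the antimalarials that Table 3 names as examples of QT-prolonging drugs. Questions 17 and 18, inside the cited range, cover heart, kidney and liver problems and family cardiac history. A locked 'eligible' flag does not oblige anyone to give the drug.

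A reader might also take 4.1 as a real conflict over whether the test is done. It is an overview contrasting test-and-treat with presumptive treatment; 7.3, Table 4 and 17.3 agree with each other, and consent covers the test. Nor are the results bound to be lost: 12.1 requires RDT results to be recorded, Appendix K has a free-text comment item, and barcoded blood spots would partly show who was tested.

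These arguments limit the consequence. They leave a locked eligibility rule that cites the wrong questions, and TPE forms with no structured field for a required test.

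**Conclusion.** The point holds as two form defects. The Appendix K rule is wrong as written at both references. Its most plausible unnoticed failure is the loss of question 20, which carries a Table 3 exclusion and has no temperature field beside it; referral under the question 20 sub-item and 7.4 would still partly protect those people. The absent 'If no' branch leaves the RDT, slide, blood spot, microtainer and referral of DP-ineligible residents without a structured record on Appendices J and K.

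The size is small. The number of people who might be wrongly marked eligible cannot be derived: it depends on how the rule is programmed and on shares of febrile, ill or medicated residents that the documents do not give. The 1 to 3 RDT positives above rest on an assumed ineligible share and a general-screening positivity rate. Power and the primary analysis are unaffected. The wording in 4.1 and 12.3 is a consistency matter only.

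**What to change.** 1. In Appendix K, change the eligibility rule to 'No' to questions 11-20 and none of the drugs in 21a-21g, keeping the 7 kg condition.
2. Add a compulsory 'If no' branch at question 22: RDT result, slide, blood spot (with reason if not done), microtainer if positive, and referral (with reason if not made). Febrile or ill people are still referred under 7.4 whatever the RDT shows.
3. Add matching counts to the Appendix J dashboards, modelled on Appendix H.
4. For consistency only, add 'except individuals not eligible for DP (see 7.3)' to 4.1 and list these microtainers in 12.3. A temperature field beside question 20 is optional.

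The cost is one corrected line, one tablet branch, a few dashboard counts and two short text edits. No procedure is added, because 7.3 and Table 4 already include the test. Section 18 lists finalizing the questionnaires as a preparation milestone, and the edits fit there.
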